8.2.1 Concomitant treatment with vitamin B6

Patients receiving vitamin B6 (pyridoxine) prior to study entry must be on a stable dose for at least 3 months prior to the screening visit. Patients who are not receiving vitamin B6 at study entry will not be allowed to initiate vitamin B6 during study participation. Patients will be encouraged not to change the dosing of vitamin B6 or discontinue vitamin B6 during study participation except for any safety events considered related to vitamin B6.

8.2.2 Prohibited medications

Patients are not allowed to receive any other investigational therapies during study participation.

Other prohibited medications are:

- **Ascorbic acid preparations:** Ascorbic acid preparations must not be used during the study period. Standard of care vitamin supplements for patients on dialysis are allowed.
- **Multiple dosing antibiotics:** Patients that require chronic antibiotics, or more than two courses of acute antibiotics, to which *O. formigenes* is sensitive will discontinue study drug and be followed for safety. If a short-term antibiotics therapy is indicated to treat acute bacterial infections, patients should receive standard of care.
 - o *O. formigenes* has shown resistance to ceftizoxime, imipenem, ampicillin, amoxicillin and penicillin. These are the preferred antibiotics for standard of care.
 - o *O. formigenes* has shown sensitivity to chloramphenicol, doxycycline, erythromycin, and tetracycline.
- **Immune suppressive therapy**

8.3 Treatment compliance

Patients will be provided with a study drug diary to record doses taken/missed. Compliance to study treatment will be questioned at each visit to the clinic. Any missed doses or doses lost during handling will be registered.

Unused medication will be returned to the clinic or site pharmacy at clinical visits weeks 6, 8, 10 and 12 during the first 14 weeks of the study. The unused medication will be accounted for an overall check of compliance.

For the continued treatment period, study drug will be returned to the clinic or site pharmacy at the next clinical visit, or the visit thereafter if new supply has not yet been received by the patient.

9 STUDY DRUG MATERIALS AND MANAGEMENT

9.1 Study drug

OC5 is the active treatment and is supplied as enteric-coated, size 4, gelatine capsules. One capsule contains NLT 1E+09 CFU. Details on the product are described in Table 7 below.

Table 7: Details of the study drug in the OC5-OL-01 study

Parameter	High Dose
Active Substance	Lyophilised O. formigenes , strain HC-1
Name	Oxabact® (OC5)
Route of Administration	Oral
Dose form	Enteric-coated capsule
Viable cell count	NLT 1E+09 CFU/dose, NMT 5E+10 CFU/dose
Excipients	Oligofructose, Maltodextrin, Alginic acid, Sucrose, Microcrystalline cellulose

9.2 Study drug packaging and labelling

Capsules will be filled into sealed aluminium tubes. A transition to tubes containing 18 capsules rather than 14 capsules was done during 2019, to include some overage medication in each tube. A desiccant will be present in the lid of the tube.

The label, including patient number, will be placed on the aluminium tube and on secondary packaging (transparent bag) holding the aluminium tubes.

The product will be labelled to meet each country's regulatory requirement.

9.3 Study drug storage

Study medication provided by the sponsor must be stored in a temperature-controlled freezer (-20°C +/- 5°C), in a locked area at site pharmacies before dispensing and delivery to patients. Study medication should be stored refrigerated (2°C to 8°C) at the patients' home, current stability data supports up to 4 weeks refrigerated storage.

9.4 Study drug accountability, handling and disposal

OxThera will supply study medication through the designated drug depot to all sites in the study.

The drug depot will complete a drug inventory log to document receipt and distribution of study drug. They will send study drug to the site pharmacies as a controlled shipment at -20°C +/- 5°C. The site pharmacies will store study medication in a temperature-controlled freezer (-20°C +/- 5°C), in a locked area. The site pharmacies will distribute study drug to patients and will inform patients that study capsules should be stored refrigerated (2°C to 8°C) at their homes in securely sealed tubes. Patients will be supplied with sufficient capsules for two weeks treatment, every second week.

Unused study medication and empty vials will be returned to the clinic or site pharmacy at clinical visits weeks 6, 8, 10 and 12 for the first 14 weeks. For the continued treatment period, remaining unused study drug and empty vials will be returned to the clinic or site pharmacy at the next scheduled visit to the clinic after each delivery of new supply. The pharmacy will document receipt of unused study medication. Any surplus of study medication will be reviewed and properly documented by the study monitor, and returned to the sponsor.

Investigational products deliberately and/or accidentally destroyed in transit or at a study site should be accounted for and documented.

10 ASSESSMENT OF EFFICACY

The main efficacy parameter to be assessed is:

- Change in total plasma oxalate level during OC5 treatment, compared with an average of the baseline values.

Secondary efficacy parameters to be assessed are:

- To evaluate the efficacy of OC5 to reduce free plasma oxalate levels during OC5 treatment in patients with Primary Hyperoxaluria (PH) who are on dialysis.
- Change in number of *O. formigenes* in faeces during OC5 treatment.
- Change in plasma oxalate values from week 10 to week 14, following the 4-week off-treatment period.
- To evaluate results from Speckle Tracking Echocardiography and traditional echocardiography for patients where this examination could be performed.

10.1 Plasma oxalate

Samples for plasma oxalate will be collected during clinical visits, as specified in Table 4: Schedule of assessments – the first 14 weeks of the study, Table 5: Schedule of assessments – continued treatment Year 1 and 2 and Table 6: Schedule of assessments Year 3. These samples have to be taken after two consecutive days of patient's standard dialysis regimen, but prior to the dialysis session on the day of sampling.

Samples for plasma oxalate will be processed at the clinical site and analysed for total plasma oxalate concentration at Academic Medical Center, Amsterdam, the Netherlands using Isotope dilution Gas Chromatography with mass selective detection (GC-MSD). Samples will also be analysed for free plasma oxalate at the University Clinical laboratory in Bonn using Ion Chromatography (IC). Each site will be provided with kits and supplies for collection, processing and shipping of blood samples for determination of plasma oxalate. Complete instructions for the collection, processing, storage and shipping of sample will be provided in the site manual. Available local lab results for free plasma oxalate performed as standard of care during the study, but before the effective date for Amendment VII (which introduced this analysis method in the protocol) will be captured retrospectively and included in the statistical analysis.

10.2 Quantification of *O. formigenes*

The possibility to monitor the natural occurrence of *O. formigenes* bacteria and the presence of the *O. formigenes* bacteria during and after treatment with OC5 is an important tool for control of the pharmacodynamics of the drug. A real-time quantitative PCR assay will be used that permits determination of the levels of *O. formigenes* and its change over time in faecal samples.

Faecal samples will be collected either at patients' home or at the clinic and shipped to central laboratory MVZ Institut für Mikroökologie GmbH, [name], Germany.

10.3 Speckle Tracking Echocardiography and Traditional Echocardiography

Speckle Tracking Echocardiography is currently evaluated as a method to detect and quantify oxalate deposits in the heart muscle.¹³ Speckle Tracking Echocardiography and traditional echocardiography will be performed at screening (alternatively before start of continued treatment) and repeated every 6 months during the continued treatment period, if possible. The examination will be performed locally using specific equipment. Images will be interpreted by a central reader who is blinded to plasma oxalate and examination date.

Speckle Tracking Echocardiography results will be evaluated for changes in Global Longitudinal Strain, including segmental changes, Short-Axis Myocardial Function, Rotational Displacement and Apical Sparing Patterns. Traditional echocardiographic parameters will also be evaluated (Ejection Fraction, End Diastolic Volume, e/é, e/a, Left Ventricular End Diastolic Dimension, Fractional Shortening, Tricuspid Regurgitation by Doppler as an indicator of RV/pulmonary pressure). A positive treatment effect would be an improved myocardial function based on the above-mentioned parameters, decreased Global Longitudinal Strain, improved Rotational Displacement and reduced/removed Apical Sparing Pattern. The treatment effect on STE parameters will be compared to traditional echocardiography parameters of LV and RV function to determine which assessment of cardiac function is more sensitive in these patients.

Speckle Tracking Echocardiography examinations performed during the study, but before this amendment's effective date will be re-evaluated to retrospectively capture the above-mentioned parameters to be included in the statistical analysis.

11 ASSESSMENT OF SAFETY

The safety parameters to be assessed are:

- Adverse Events
- Laboratory safety measurements

11.1 Definition of Adverse Events

Adverse Event (AE)

An AE is any untoward medical occurrence in a patient or clinical study patient administered a pharmaceutical product and which does not necessarily have a causal relationship with this treatment. An AE can therefore be any unfavourable and unintended sign (including abnormal laboratory finding), symptom, or disease temporally associated with the use of a medicinal (investigational) product, whether or not related to the medicinal (investigational) product. AEs therefore include e.g. worsening of a pre-existing illness and any injury or accident. This refers also to symptoms due to a pre-existing allergy, e.g. if seasonal allergy symptoms are within what is normally experienced they should not be recorded as adverse events. If the symptoms are worse than what is normally experienced, then they should be recorded as adverse events.

An AE does **not** include:

- Symptoms of the underlying disease that might be reasonably anticipated to come and go, or progress, given the nature and severity of the condition. However, if the progression of the disease escalates and results in hospitalisation, is life-threatening, or is fatal, then progression of the disease should be reported as an AE of serious nature;
- Expected variations in severity of disease signs and symptoms that have previously been reported in the patient's medical history;
- Pre-planned medical or surgical procedures (e.g., surgery, tooth extraction, or transfusion) [Note: The condition that leads to the procedure may be an AE];
- Overdose of study drug without any clinical signs or symptoms; or
- Clinically significant laboratory values. If abnormal laboratory values are accompanied by abnormal signs or symptoms, the signs or symptoms are considered an AE and should be recorded as such. Abnormal laboratory values associated with the underlying disease are not an AE unless the values unexpectedly worsen. Abnormal laboratory values will be recorded in the study database.

Adverse Drug Reaction (ADR)

An AE is defined as an adverse drug reaction (ADR) if further analyses prove that the AE is caused or partially caused by the investigational product. This includes interaction, overdosing, abuse and development of addiction. Expected ADRs are also possible events due to the substance class of the investigational drug, expected from analogue conclusions or theoretical considerations related to toxicological, pharmacological or kinetic characteristics.

Serious Adverse Event (SAE)

A Serious Adverse Event (SAE) is one that suggests a significant hazard, contraindication, side effect or precaution that results in:

- the patient's death
- is life-threatening*
- requires inpatient hospitalisation or prolongation of existing hospitalisation**
- persistent or significant disability/incapacity; or

- congenital anomaly/birth defect
- corresponds to other important medical event as determined by the Investigator.
 - * Life threatening means that the patient was at immediate risk of death from the AE as it occurred or it is suspected that the use or continued use of the investigational product would result in the patient's death. Life threatening does not mean that had an AE occurred in a more severe form it might have caused death.
 - ** Hospitalisation requires over-night stay at the hospital. Outpatient treatment in an emergency room is not itself a SAE. Hospital admission and/or operations planned before or during a study are not considered SAEs if the illness or disease existed before the patient was enrolled in the study, provided that it did not deteriorate in an unexpected way during the study.

Suspected Unexpected Serious Adverse Reaction (SUSAR)

Suspected Unexpected Serious Adverse Reaction (SUSAR) is a suspected unexpected serious adverse reaction

In cases of doubt on this issue, it is suggested that there should be a predisposition to report rather than not to report (see section 11.4).

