11.3 Recording Adverse Events

Each patient will be questioned about AEs at each clinic visit/ following initiation of treatment. The question asked will be "Since your last clinic visit have you had any health problems?" The information can also be obtained from signs and symptoms detected during each examination, observed by the study personnel or spontaneous reports from the study patients or by lab results.

The investigator is to record in the CRFs all directly observed AEs, all AEs as a response of the open question and all AEs spontaneously reported by the patient during the study.

The investigator will record all AEs by:

- Description of event (recorded in standard medical terminology and avoiding abbreviations),
- Start and end date,
- Intensity* (mild, moderate or severe),
- Seriousness (serious or not serious, according to definition),
- Causal relationship, (definitely, possible, probable, unrelated)
- Action taken, (none, treatment required, patient withdrawn, other)
- Outcome of the AE (recovered, recovered with sequelae, death, not recovered)

The Sponsor or delegate will code all AEs and SAEs using MedDRA.

* For each reported AE, the intensity will be recorded. The following definitions of intensity are to be used:

- Mild: A mild AE means awareness of symptoms or signs, but easily tolerated (acceptable).
- Moderate: A moderate AE means enough discomfort to interfere with usual activity (disturbing).
- Severe: A severe AE means incapacity to work or to do usual activity (unacceptable)

If the intensity changes within 24 hours the maximum intensity should be recorded. If the intensity changes over a longer period of time, the changes should be recorded in the CRF.

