11.5.3 Elevated levels of plasma formate

Since *Oxalobacter formigenes* converts oxalate to formate, there may be the possibility of elevated plasma formate levels following administration of high doses of OC5. Formate is a metabolite of methanol responsible for the toxicity observed with methanol poisoning. Typically, toxic effects require prolonged exposure to elevated plasma formate levels.

Previous studies with Oxabact® (including OC2, OC3 and OC5) in over 100 patients with doses ranging from NLT 10⁷ to NLT 10⁹ CFU have not indicated any signs or symptoms of elevated formate plasma levels, metabolic acidosis or methanol poisoning. The main manifestations of methanol poisoning are metabolic acidosis and ocular toxicity. Any patient who develops signs and symptoms of metabolic acidosis should be evaluated to identify the source (e.g. evaluation of serum bicarbonate, blood pH, anion gap, osmolality gap and plasma formate).

Formate accumulation in plasma is the main reason for acidosis in early, uncomplicated stages of metabolic acidosis.¹⁴ Metabolic acidosis is characterised by low blood pH (arterial pH < 7.38 or venous pH < 7.34) or low levels of serum bicarbonate, HCO₃⁻ (< 18 mmol/L). Decreased levels of serum bicarbonate or blood pH will serve as an indication of elevated levels of formate. The OC5-OL-01 study will investigate these early signs of elevated plasma formate as part of routine safety labs. Low levels of serum bicarbonate or blood pH should trigger determination of the anion gap and the osmotic gap in order to confirm or rule out the diagnosis of metabolic acidosis due to elevated formate levels.

If metabolic acidosis is diagnosed, the acidosis should be corrected as quickly as possible and therapy provided, if appropriate. If a diagnosis due to elevated formate levels cannot be excluded or if the metabolic acidosis cannot be corrected by standard of care the study medication should be stopped until further evaluation. Further evaluation should then include levels of plasma formate and visual disturbance test.

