12 STATISTICS

12.1 Statistical methods

Efficacy: The primary endpoint, change in total plasma oxalate from baseline, will be evaluated over time for each patient. Evidence for efficacy will be provided as the combined evaluation of individual case studies. Plasma oxalate levels will be measured on a monthly basis throughout the first 24 months of the continued treatment period and once every 3-4 months during the last 12 months of the continued treatment period. All secondary endpoints will be analysed using the same methodology.

For the primary endpoint the change in total plasma oxalate levels will be based on the average from two baseline measurements (week 2 and week 4) and one measurement every 4th week throughout the first 24 months of the continued treatment period and every 3-4 months during the last 12 months of the continued treatment period.

The change in plasma oxalate during 4 weeks follow-up period after the end of the 6 weeks treatment period with OC5, will be based on one measurement at week 10 and one measurement at week 14. The last observation will be carried forward in case of missing values at week 14 and/or week 10.

Two interim analyses will be performed: The first analysis will be based on patients who complete the first year of continued treatment. The second interim analysis will be based on all study data obtained up to 24 months. Both interim analyses will evaluate all captured efficacy and safety parameters.

The individual changes in plasma oxalate per week will also be calculated as an average slope using regression of plasma oxalate by week.

The study involves a small number of patients and natural history data on changes in total and free plasma oxalate for this population is limited. Response to treatment is likely to vary depending on the baseline plasma oxalate level, individual hepatic oxalate production and age of each patient. Accordingly, the sample size is not based on assumptions of efficacy outcome and statistical power, and the definition of analysis populations is not applicable. Any inferences from the data will be based on clinical relevance rather than statistical significance.

Safety: The safety will be summarised using descriptive statistics based on frequency, seriousness and severity of treatment emergent AEs. Clinically relevant changes in safety laboratory parameters will also be summarised.

All statistical analyses will be further defined in a Statistical Analysis Plan.

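### Protocol 11.1 both includes and excludes laboratory abnormalities as AEs, and the SAP plans no count of clinically significant laboratory values to cover the gap

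*Protocol*

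**What the plan says.** **AE definition (protocol 11.1).** The opening is inclusive: "An AE can therefore be any unfavourable and unintended sign (including abnormal laboratory finding), symptom, or disease". The list of what an AE does not include then contains "Clinically significant laboratory values. If abnormal laboratory values are accompanied by abnormal signs or symptoms, the signs or symptoms are considered an AE". Later in the same item: "Abnormal laboratory values associated with the underlying disease are not an AE unless the values unexpectedly worsen". The item ends by keeping abnormal values in the study database.

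**AE recording (protocol 11.3).** AE information may come from examination findings, staff observation, "spontaneous reports from the study patients or by lab results".

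**Formate (protocol 11.5.3).** "Decreased levels of serum bicarbonate or blood pH will serve as an indication of elevated levels of formate". And: "The OC5-OL-01 study will investigate these early signs of elevated plasma formate as part of routine safety labs". Limits are given: bicarbonate below 18 mmol/L, arterial pH below 7.38, venous pH below 7.34. A low value leads to further tests to confirm or rule out acidosis due to formate.

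**Analysis.** Protocol 12.1 states: "Clinically relevant changes in safety laboratory parameters will also be summarised". SAP 6.7.1 builds every AE table from reported AEs. SAP 6.7.2 gives per-visit descriptive statistics and change from baseline for the laboratory panel, which includes bicarbonate and pH/CO2. It also gives a per-patient listing of out-of-range values with the investigator's judgement of clinical significance (14.3.4.1 in SAP 10.3). Unscheduled samples are listed only.

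**The concern.** An investigator cannot apply both halves of 11.1 to the same result. Taken at its word, the exclusion removes the laboratory values judged to matter most, and two investigators could record the same result differently.

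More than a count is involved. Intensity, seriousness and causality are recorded for AEs (11.3). An adverse drug reaction is defined as a kind of AE (11.1), and unresolved reactions are to be followed (7.3, 11.4). A value not recorded as an AE gets no AE causality assessment and does not enter that follow-up rule. Formate accumulation is the one mechanism-based risk that the protocol proposes to detect through routine laboratory tests. It calls a low bicarbonate or pH an early sign, so the sign may come before any symptom, and that is the situation in which the exclusion applies.

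**Working it through.** The plan gives no figure to reproduce. The check sets the rules side by side and then asks what the SAP would show.

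**Step 1: which laboratory abnormalities can reach the AE tables?**

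| Situation | Rule | AE? |
|---|---|---|
| Abnormal value with signs or symptoms | 11.1, excluded item | The signs or symptoms are; the value is not |
| Disease-related value that unexpectedly worsens | 11.1, same item | Yes |
| Metabolic acidosis diagnosed after the tests in 11.5.3 | 11.1 opening (a disease) | Can be recorded |
| Clinically significant value, no symptoms, no diagnosis, not attributed to the underlying disease | 11.1 opening and 11.3 against 11.1 excluded item | Contradictory; literally excluded |

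Only the last row is at risk. The exception for unexpected worsening is written for disease-related values. A new value not attributed to the disease has no explicit route back in, apart from the opening sentence that the exclusion contradicts.

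**Step 2: does the SAP repair this?** No SAP rule turns a laboratory abnormality into an AE, so whatever was not recorded as one is absent from 14.3.1.1 to 14.3.1.6.

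**Step 3: is the summary promised in 12.1 planned?** SAP 10.3 has the out-of-range listing (14.3.4.1) and the raw and change-from-baseline tables (14.3.4.2 to 14.3.4.4). It has no count of patients with clinically significant values, no shift table and no threshold table, and SAP section 7 does not declare the promised summary as dropped. SAP 6.7.5, by contrast, does tabulate clinically significant and not clinically significant findings for physical examination.

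**Step 4: what do the planned statistics show?** If one of 12 patients falls by *d* at a visit and the others do not change, the mean changes by *d*/12, about 8% of that patient's change. SAP 6.1 also prints the minimum, which would show an extreme scheduled value. The minimum does not say how many patients were affected, whether it is the same patient across visits, or whether the value was judged clinically significant. It also leaves out unscheduled samples, where a repeat test may fall.

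**Step 5: weight of one case.** Protocol 11.5.1.2 reports 12 treated patients. The exact (Clopper-Pearson) 95% limits for *x* of *n* are the 0.025 quantile of Beta(*x*, *n* − *x* + 1) and the 0.975 quantile of Beta(*x* + 1, *n* − *x*), with a lower limit of 0 when *x* = 0.

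- Recorded: 1/12 = 8.3% (0.2% to 38.5%).
- Not recorded: 0/12 = 0% (0% to 26.5%).

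This is an illustration; the documents report no such case.

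**The case against.** The strongest reply is that laboratory safety has its own reporting stream. Protocol section 11 and SAP 5.3 name AEs and laboratory measurements as separate safety parameters. The values are kept, summarised and listed with the investigator's judgement, so nothing is lost from the report. A low bicarbonate or pH is also not left as a bare number, because 11.5.3 sends it to further testing and a diagnosed acidosis can be recorded. The exclusion may be a drafting slip for values that are not clinically significant. Finally, a protocol change comes late: one patient remained in September 2019, and rewording now would mix two AE definitions in one dataset.

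Most of this stands, and it limits the point. A reader might infer that the SAP only lists out-of-range values; SAP 6.7.2 shows otherwise. A reader might infer that every symptom-free clinically significant value is excluded, or that formate acidosis would go unseen; the routes in 11.1, 11.3 and 11.5.3 and the laboratory outputs do not support that. Nor do the documents show that any event has been missed.

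The reply leaves three things open. The two statements in 11.1 still conflict, and nothing in the documents says the exclusion is a slip. The AE tables can still omit a symptom-free value. The summary promised in 12.1 is met only by general descriptive statistics and a listing.

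**Conclusion.** The point holds in limited form. Protocol 11.1 contradicts itself and sits badly with 11.3 and 11.5.3, so a symptom-free, clinically significant laboratory value can be absent from the TEAE, relatedness and severity tables. It is not absent from the database, the laboratory summaries or the out-of-range listing. The SAP plans no count that would bring such values together, despite the commitment in protocol 12.1.

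The number of affected values cannot be obtained from the documents. The scale in the AE tables is one case in 12, or 8.3 percentage points of incidence. This assumes that investigators apply the exclusion literally and that no diagnosis or symptom brings the event back in. It is worth correcting because the correction uses recorded data and the study has no control arm against which to set a low AE count.

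**What to change.** **SAP 6.7.2 and 10.3.** Add one table with two parts:

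1. The number of patients with at least one post-baseline value judged clinically significant, by parameter and including unscheduled samples, from the judgement already recorded for 14.3.4.1.
2. The number of patients with bicarbonate or pH below the limits in protocol 11.5.3, also including unscheduled samples. This part does not depend on the investigator's judgement. The pH limits differ for arterial and venous blood, and the SAP panel does not say which was taken. Use the sample type if it is recorded; otherwise show the count under each limit.

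In both parts, mark patients who already met the criterion at baseline, since abnormal values may be part of the underlying disease.

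**Protocol.** Sections 11.1, 11.3 and 11.5.3 must be reconciled into one rule for when a laboratory abnormality is recorded as an AE. Under protocol section 19 this needs an amendment with ethics and regulatory approval, and it can affect only the recording still to come.

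**Study report.** State that the AE tables may omit symptom-free laboratory abnormalities and should be read with the new table.

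**Cost.** One extra table from data already collected, and a safety summary that may look slightly less favourable.
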